4. STUDY POPULATION

4.1. INCLUSION CRITERIA

Patients must satisfy all the following inclusion criteria before they are allowed to participate in the study:

1. Patients must give written informed consent (personally signed and dated) before completing any study-related procedure
2. Histologically or cytologically confirmed recurrent and/or metastatic squamous cell carcinoma of the oral cavity, oropharynx, hypopharynx or larynx
3. Documented progressive disease after chemotherapy for locoregionally advanced or recurrent / metastatic SCCHN which included a platinum derivative (cisplatin or carboplatin) that is not suitable for local therapy. Platinum-based chemotherapy can have been associated with cetuximab.

Eligible patients include one of the following categories (see Appendix 9 for diagram):

- patients who have received induction chemotherapy (ICT) consisting of cisplatin plus 5-fluorouracil or docetaxel plus cisplatin plus 5-fluorouracil followed by radiotherapy alone or chemoradiation (CRT) or radiotherapy concomitant with cetuximab provided that recurrence occurs within 6 months of completing local therapy
- patients who have completed cisplatin-based CRT with or without ICT provided that

recurrence occurs within 6 months of completing local therapy. The minimum cumulative dose of cisplatin during CRT must be 200 mg/m².

- patients with recurrent and/or metastatic SCCHN who relapse after platinum-based (cisplatin or carboplatin) chemotherapy given in first-line with an interval < 12 months
- patients with metastatic SCCHN at diagnosis who have been treated with platinum-based (cisplatin or carboplatin) chemotherapy in first-line and relapse with an interval < 12

months.

The definition of failure is as follows:

- refractory disease: progression during platinum-based regimen
- resistant disease: progression during the time from completion of platinum-based chemotherapy but < 6 months after its completion
- or other type of failure: progression \geq 6 months but < 12 months after completion of platinum-based chemotherapy

4. No more than one prior chemotherapy regimen for recurrent/metastatic disease. Prior treatments with targeted therapy used in monotherapy are allowed

5. Minimum interval of 4 weeks between the completion of first-line chemotherapy and randomisation

6. Measurable or non measurable disease

7. WHO performance status \leq 1

8. Age \geq 18 years and < 80 years

9. Adequate haematological function: absolute neutrophil count (ANC) \geq 1.5 x 10⁹/L, platelets \geq 100 x 10⁹/L, haemoglobin \geq 10g/dL.

10. Adequate hepatic function: transaminases \leq 2.5 x Upper Limit of Normal (ULN), total bilirubin \leq 1.5 x ULN, alkaline phosphatase \leq 5 x ULN

11. Adequate renal function: calculated (Cockcroft-Gault) creatinine clearance > 60 ml/min

12. Women of childbearing potential must be using a medically accepted method of contraception (barrier methods, oral contraceptives, intrauterine devices) to avoid pregnancy during the 2 months preceding the start of study treatment, throughout the study period and for up to 3 months after the last dose of study treatment in such a manner that the risk of pregnancy is minimised. Women of childbearing potential must have a negative serum or urine pregnancy test within 72 hours prior to first treatment administration

13. Fertile men must be using adequate contraceptive measures throughout the study period and for up to 3 months after the last dose of study treatment if their partner are women of childbearing potential

14. The patient must have access to social insurance if applicable in the local regulations

15. Absence of any psychological, familial, sociological or geographical condition potentially hampering compliance with the study protocol and follow-up schedule, those conditions should be assessed with the patient before registration in the trial.

4.2. EXCLUSION CRITERIA

If any of the following apply, the patient must not enter into the study:

1. Nasopharyngeal carcinoma
2. History of brain or leptomeningeal involvement
3. History of other cancers except other synchronous head and neck squamous cell carcinomas, adequately treated in situ carcinoma of the cervix uteri, basal or squamous cell carcinoma of the skin or other cancer curatively treated with surgery and/or radiotherapy (with or without other anti-cancer therapy) and with no evidence of disease for at least 3 years
4. Albumin level < 35 g/L
5. Patients with weight loss \geq 5% within the last 3 months

6. Recurrent pulmonary or upper airways infections (3 times or more in the last 3 months) requiring antibiotics and/or any infection requiring antibiotics within the last month before study entry
7. Grade ≥ 2 peripheral neuropathy at study entry according to NCI-CTC AE (version 3.0)
8. Serum potassium < the lower limit of normal
9. ECG demonstrating a QT/QTc interval > 480 msec
10. A female is not eligible to enter the study if :
 - . Pregnant or lactating
 - . With positive pregnancy test at inclusion
11. Female of childbearing potential who is unwilling or unable to use a medically accepted method to avoid pregnancy during the 2 months preceding the start of study treatment, throughout the study period and at least 3 months following the last dose of study treatment
Male unwilling or unable to use a medically accepted method to avoid pregnancy throughout the study period and at least 3 months following the last dose of study treatment if their partners are women of childbearing potential
12. Patients with any underlying medical condition that might be aggravated by treatment or which cannot be controlled i.e. active serious infection, poorly controlled diabetes mellitus, concurrent heart failure [New York Heart Association (NYHA) class III-IV] or with progressive or unstable angina, myocardial infarction within 6 months, and/or poorly controlled hypertension.
13. "Third space" fluids (pleural effusion, ascites, massive edema)
14. Concomitant treatment with any other anti-cancer therapy and contraindicated medication (see Section 6.1)
15. Prior treatment with vinca-alkaloids and methotrexate
16. Participation into a clinical study of an investigational agent within 30 days before study entry

4.3. NUMBER OF PATIENTS

An estimated sample size of 265 randomized patients in each arm was expected, i.e. a total of 530 randomised patients. The required number of events to observe at the final analysis is 437 deaths. An approximately 19 months accrual period was planned.

Following the decision to stop the recruitment, 459 patients have actually been enrolled in this study with a 1:1 ratio for randomization.

The details of the original sample size are given in Section 11.1.

5. STUDY TREATMENT

5.1. STUDY DRUG ADMINISTRATION

5.1.1. Vinflunine and methotrexate (arm A)

Descriptions of study drugs, storage, packaging, labelling and drug accountability are given in Section 10.

Patients randomised to arm A will receive vinflunine on day 1 as a 20 minute IV infusion at 280 mg/m² and methotrexate on days 1 and 8 as a bolus intravenous injection at 30 mg/m² of every three-week cycle.

The total dose to be given will be calculated according to body surface area (BSA). In calculating BSA, actual heights and weights should be used. BSA should be recalculated prior to the next cycle dosing.

5.1.1.1. *Vinflunine*

The calculated dose of vinflunine will be administered as follows:

1. Mix vinflunine in a 100 mL bag of normal saline (NS) or 5% glucose solution.
2. **Establish venous access on a large vein preferably in the upper part of the forearm or using a central venous line (CVL).**

The veins of the dorsum of the hand and veins close to joints should be avoided.

3. Start a venous infusion of 500 mL bag of NS or 5% glucose solution at a free-flowing rate to assess the patency of the vein.
4. Infuse the vinflunine over 20 minutes. Piggy-back the vinflunine infusion to the side injection port closest to the 500 mL NS or 5% glucose solution bag. This allows the vinflunine to be further diluted during administration.
5. Assess for patency frequently during the infusion,
6. Maintain extravasation precautions throughout the infusion.
7. After vinflunine infusion is completed (the line must be totally drained), run the remaining NS or 5% glucose solution bag at a flowing rate of 300 mL/hour (volume of at least 100 ml) for flushing the vein.

5.1.1.2. *Anti-emetic and laxative prophylaxis*

- Antiemetic prophylaxis will consist of a single dose of dexamethasone 8 mg or an equivalent dose of methylprednisolone just before each infusion.

- Administration of vinflunine requires addition of dietary measures and laxatives, to avoid potentially serious constipation, **starting the day of each vinflunine administration (day 1) to day 5 as follows:**

- Dietary measures including proper dietary fluid and fibre intake:
 - Oral hydration: at least 1.5 litres of water per day.
 - Diet containing high fibre foods (10 to 20 g of bran, whole-wheat breads and cereals or 5 fresh or cooked vegetables or fruits)
- Administration of laxatives listed below :
 - predominantly stool softener : lactulose, polyethylene glycol, docusate sodium, milk of

magnesium or mineral oil (paraffin)

- or predominantly stimulant : senna derivatives, cascara or bisacodyl.

Dose for laxatives are per investigator discretion. Use of other laxative treatment is allowed upon prior sponsor approval.

For patients considered at increased risk of serious constipation, defined as:

- History of chronic or refractory constipation,
- Concomitant treatment with opioids,
- Peritoneal carcinomatosis or abdominal tumour masses,
- Persistent symptoms under vinflunine despite the days 1 to 5 dietary measures and laxatives administration,

the use of a stool softener and a stimulant is recommended to maximise efficacy (Droney J, 2008).

Mouthwash is recommended as prophylaxis of stomatitis.

5.1.1.3. Methotrexate

Mouthwash is recommended as prophylaxis of stomatitis.

On day 1, methotrexate will be administered by direct bolus injection through the side arm of the remaining NS or 5% glucose solution bag after completion of vinflunine infusion.

On day 8, methotrexate will be administered through the side arm of a freely running NS or 5% glucose solution IV infusion.

5.1.2. Methotrexate (arm B)

Descriptions of study drug, storage, packaging, labelling and drug accountability are given in section 10.

Patients randomised to arm B will receive methotrexate on a weekly basis as a bolus intravenous injection at the dose of 40 mg/m²/week. The drug will be administered by direct injection through the side arm of a freely running NS or 5% glucose solution IV infusion.

One cycle of methotrexate is defined as a three-week period, i.e. 3 weekly administrations of methotrexate (days 1, 8, and 15).

5.2. GUIDELINES FOR TREATMENT MODIFICATIONS

Treatment will be modified in case of dose limiting haematological and/or non haematological toxicity. Dose adjustment and/or treatment delay are to be made according to the body system showing the greatest degree of toxicity. Toxicities will be graded according to the NCI Common Terminology criteria for Adverse Events (version 3.0).

5.2.1. General considerations

After any dose reduction, this dose is then maintained with no re-escalation of doses in subsequent cycles.

Re-treatment may be delayed by one week up to 2 weeks pending recovery. Any patient who requires a delay of more than 2 weeks, for whatever reason, will be taken off study.

In case of toxicity, all dosing adjustment or delay should be applied to both drugs of arm A unless there is another specific recommendation.

5.2.2. Vinflunine (arm A)

5.2.2.1. Dose modifications

Guidelines which have to be applied for dose modifications are detailed in Table 4.

The dose of i.v. vinflunine may be decreased depending on how well the patient tolerates the study drug. Dose of i.v. vinflunine will be reduced as described below.

Table 4: Dose reduction of IV vinflunine

Dose Level	Vinflunine
0 (starting dose)	280 mg/m ²
-1	250 mg/m ²
-2	225 mg/m ²

Patients requiring dose reductions below dose level -2 must discontinue study drug with the following exception: patients with responding disease after consultation and approval by the sponsor.

5.2.2.2. Treatment modifications for haematological toxicity

Complete blood cell counts will be performed on days 1 and 8 of each cycle during the treatment period. If a patient experienced fever (temperature $\geq 38^{\circ}\text{C}$) and/or developed infection, blood cell count should be immediately performed.

Cycle delay

Cycle is considered delayed if Day 1 treatment has been performed:

- either $\geq 21 + 4$ days since last Day 1 study drug administration (i.e., Day 26 or more).
- or $\geq 14 + 4$ days since last Day 8 study drug administration

Neutrophil count should be $\geq 1.5 \times 10^9/\text{L}$ (grade 1) and platelet count $\geq 100 \times 10^9/\text{L}$ before each new cycle.

Table 5 details haematological toxicity which must result in cycle delay.

Table 5: Dose delay for haematological toxicity on day 1 of each cycle

Haematological toxicity on scheduled day 1			Day 1 administration of study treatment
Absolute neutrophils		Platelets	
$\text{ANC} \geq 1.5 \times 10^9/\text{L}$	And	$\geq 100 \times 10^9/\text{L}$	No dose modification. Treat on time
$\text{ANC} < 1.5 \times 10^9/\text{L}$	And/Or	$< 100 \times 10^9/\text{L}$	Delay one week and reassess

If recovery has not occurred after a 2-week delay, the treatment will be discontinued unless approved by the sponsor.

Dose modifications

Table 6 details haematological toxicity which must result in dose reduction.

Table 6: Dose modifications for haematological toxicity

Haematological toxicity during the previous cycle	Dose adjustment for next cycle
---	--------------------------------

Grade 3 thrombocytopenia (platelets $\geq 25 \times 10^9/L$ and $< 50 \times 10^9/L$) with significant bleeding or requiring transfusion	
First appearance : decrease one dose level
 
Second appearance : decrease one dose level
 
Third appearance : stop treatment

Grade 4 thrombocytopenia (platelets $< 25 \times 10^9/L$)	
Grade 4 neutropenia (ANC $< 0.5 \times 10^9/L$) lasting ≥ 5 days	
Neutropenic infection (grade ≥ 3 neutropenia concomitant with grade ≥ 3 infection)	
Febrile neutropenia of any grade	

5.2.2.3. *Treatment modifications for non-haematological toxicity*

Based on prior clinical experience of i.v. vinflunine, non-haematological adverse events which may require treatment modification include :

- nausea and vomiting
- constipation
- stomatitis
- and peripheral neuropathy.

Therefore, specific recommendations for treatment modifications for each of these adverse events are provided in this section.

Rare cases of Posterior Reversible Encephalopathy Syndrome (PRES) have been observed after administration of vinflunine. The typical clinical symptoms and signs are, with various degrees: neurological (headache, confusion, seizure, visual disorders), systemic (hypertension), and gastrointestinal (nausea, vomiting). Radiological signs are white matter abnormalities in the posterior regions of the brain. Clinical and radiological features usually resolved rapidly without sequelae after treatment discontinuation.

Vinflunine must be discontinued in patients who develop neurological signs of PRES.

Cycle delay

Rules defining the cycle delay are the same as outlined in section 5.2.2.2.

All non-haematological toxicity, except alopecia and fatigue should be resolved to grade ≤ 1 prior to starting a new cycle of treatment.

If grade ≥ 3 toxicity persists for more than 2 weeks, the study drug should be permanently discontinued.

Dose modifications

The table below outlines dose modifications for non-haematological toxicity.

Table 7: Dose modifications for non-haematological toxicity

Non haematological toxicity during the previous cycle	Dose adjustment for next cycle
Constipation	
Grade 2	Maintain treatment at the same dose Adjust laxative therapy*
Grade 3	Decrease one dose level Adjust laxative therapy*
Grade 4	Discontinue treatment
Stomatitis	
Grade 2	Maintain treatment at the same dose
Grade ≥ 3	Decrease one dose level
Peripheral neuropathy	
Grade 2	Decrease one dose level
Grade ≥ 3	Discontinue treatment
Other grade $\geq 3^{**}$ toxicities	To be adjusted as medically indicated after discussion between investigator and sponsor
Hyperbilirubinemia	
Grade 2 ($> 1.5 \times \text{ULN}^{***}$ and $\leq 3.0 \times \text{ULN}$)	Decrease dose to 250 mg/m^2
Grade 3 ($> 3.0 \times \text{ULN}$)	Delay treatment until recovery to grade 2 and resume at 250 mg/m^2
Decreased creatinine clearance (Cockcroft-Gault)	
$< 40 \text{ ml/min}$ and $\geq 20 \text{ ml/min}$	Decrease dose to 250 mg/m^2
$< 20 \text{ ml/min}$	Discontinue treatment

* Give a stimulant and a stool softener

** Except grade 3 fatigue

*** Upper limit of normal

5.2.3. Methotrexate in Arm A

5.2.3.1. Dose modifications

The following dose levels will be used in modifying the dose of methotrexate in arm A:

Table 8: Dose reduction of methotrexate in Arm A

Dose level	Methotrexate
0 (starting dose)	30 mg/m ²
- 1	20 mg/m ²

Patients requiring dose reductions to less than 20 mg/m² must be discontinued with the exception of responding patients after consultation and approval by the sponsor.

5.2.3.2. Treatment modifications for haematological toxicity

Complete blood cell counts will be performed before each administration of methotrexate.

Cycle delay

Cycle is considered delayed if Day 1 treatment has been performed:

- either $\geq 21 + 4$ days since last Day 1 study drug administration (i.e., Day 26 or more).
- or $\geq 14 + 4$ days since last Day 8 study drug administration

Neutrophil count should be $\geq 1.5 \times 10^9/L$ (grade 1) and platelet count $\geq 100 \times 10^9/L$ before each new cycle (day 1 administration) as shown below.

Table 9: Arm A- Dose delay of methothrexate on day 1 for haematological toxicity

Haematological toxicity before day 1 administration			Day 1 administration of study treatment
Absolute neutrophils		Platelets	
ANC $\geq 1.5 \times 10^9/L$	and	$\geq 100 \times 10^9/L$	No dose modification. Treat on time
ANC $< 1.5 \times 10^9/L$	and / or	$< 100 \times 10^9/L$	Delay cycle and reassess one week later

Dose delay / cancellation of methotrexate at day 8

If neutrophils count are $< 1.5 \times 10^9/L$ and/or platelets count $< 100 \times 10^9/L$, the day 8 administration should be delayed 1 week, to day 15. If no recovery after reassessment one week later, the dosing should be cancelled (Table 10).

This protocol does not allow other cases of dosing delay of methotrexate. Any delay of a methotrexate dosing done outside of this above rule (also shown in Table 10) will be recorded as a delay and as a protocol deviation, (≥ 4 days with respect to the planned day).

Table 10: Dose delay or cancellation of methotrexate at Day 8 in Arm A

Haematological toxicity before administration			
Absolute Neutrophils		Platelets	Day 8
$ANC \geq 1.5 \times 10^9/L$	and	$\geq 100 \times 10^9/L$	Treat on time
$ANC < 1.5 \times 10^9/L$	and / or	$< 100 \times 10^9/L$	Delay 1 week and reassess. If no recovery, dose must be cancelled

Dose modifications

Table 11 details severe haematological toxicity which must lead to dose reduction.

Table 11: Dose modifications of methotrexate for haematological toxicity in Arm A

Haematological toxicity after the previous administration	Dose adjustment for next administration
Grade 3 thrombocytopenia (platelets $\geq 25 \times 10^9/L$ and $< 50 \times 10^9/L$) with significant bleeding or requiring transfusion	First appearance : reduce one dose level
Grade 4 thrombocytopenia (platelets $< 25 \times 10^9/L$)	
Grade 4 neutropenia (ANC $< 0.5 \times 10^9/L$) lasting ≥ 5 days	
Neutropenic infection (grade ≥ 3 neutropenia concomitant with grade ≥ 3 infection)	Second appearance: stop MTX
Febrile neutropenia of any grade	

5.2.3.3. *Treatment modifications for non-haematological toxicity*

The non haematological adverse events which may require treatment modifications include:

- stomatitis
- increased transaminases
- and less often, nausea, vomiting, diarrhoea and skin rash.

Cycle delay

Rules defining the cycle delay are the same as outlined in section 5.2.3.2.

Day 1 administration must be delayed in case of grade > 1 stomatitis or grade > 1 increase of transaminases (> 2.5 x ULN). Methotrexate must not be readministered before total recovery.

If recovery requires more than 2 weeks, methotrexate should be permanently discontinued.

Dose cancellation

Administration on day 8 must be cancelled in case of grade > 1 stomatitis or grade > 1 increase of transaminases (> 2.5 x ULN).

The protocol does not allow Day 8 dosing delay of methotrexate in case of non-haematological toxicity. Any delay of a methotrexate Day 8 dosing will be recorded as a delay and as a protocol deviation if it has been performed $\geq 7 + 4$ days since last Day 1 study drug administration (i.e., Day 11 or more).

Dose modifications

The table below outlines dose reduction for non-haematological toxicity.

Table 12: Dose modifications of methotrexate in Arm A for non-haematological toxicities

Non haematological toxicity after the previous administration	Dose adjustment for next administration
Stomatitis Grade 1 Grade 2 Grade \geq 3	Maintain the same dose Decrease one dose level Discontinue MTX
Transaminases > 2.5 x ULN and \leq 5.0 x ULN > 5.0 x ULN and \leq 20 x ULN	Decrease one dose level Discontinue MTX
Decreased creatinine clearance (Cockcroft-Gault) \leq 60 mL/min and \geq 20 mL/min < 20 mL/min	Decrease one dose level Discontinue treatment
Other grade \geq 3* toxicities	To be adjusted as medically indicated

* except grade 3 fatigue

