
Criteria for evaluation:
 
- Efficacy assessment:
 
The primary efficacy endpoint will be the overall survival defined as time from randomisation to death or last follow-up.
 
Secondary endpoints include the response and disease control rate by using RECIST (version 1.1), the response and disease control duration and the progression-free survival.
 
- Safety assessment will be assessed by:
 
 . physical examination . regular reporting of adverse event by using NCI CTC AE (version 3.0) 
ECG to be performed on day 1 of cycle 1 before and after drug administration in both arms. Thereafter, ECG will be performed before drug administration every 2 cycles in both arms. After review of safety data including ECG results by the IDMC, the need for repeated ECGs before each cycle can be revised.
 
 . complete blood cell counts performed on days 1 and 8 of each cycle in arm A and before each weekly administration in arm B . serum biochemistry including AST, ALT, alkaline phosphatase, total bilirubin, urea, creatinine, calculated creatinine clearance, glucose, calcium, sodium, potassium, magnesium, chloride, bicarbonate, total protein and albumin. Tests will be performed every 3 weeks, except glucose, total protein and albumin which will be performed every 6 weeks in both arms. 
- Patient-reported outcomes will be assessed by using the QLQ-core 30 EORTC questionnaire and the QLQ-Head and Neck 35 EORTC module.
	

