
End of study
 
The end of study is the date of the last patient study treatment administration plus 30 days.
 
No follow-up visit will be performed. At the time of the amendment PA11:
 
 - Patients under treatment will stop the study at the EOT. - Patients under follow-up will stop immediately. 	

Study L00070 IN 309 F0
	

Table 1: Study flow chart

Required assessments	Screening period	Treatment period		End of treatment (f)	Follow-up (g)
	Day - 21 to - 1	Day 1 every cycle	Every 6 weeks		
Signed informed consent	X (a)				
Demographic data					
Demography/Medical History/Diagnosis	X				
Serum or urine pregnancy test in women of childbearing potential	X (j)				
Physical Examination/Vital signs/Weight	X (b)	X		X	
WHO Performance Status	X (b)	X		X	X
Safety					
Electrocardiogram (ECG)	X (m)	X (m)			
Pre-treatment events/Adverse events/SAE	X (k)	X		X	X
Complete blood cell count (l)	X (b)	X (c) (within 24 hours)		X	
Blood chemistry (d)	X (b) (e)	X	X (e)	X (e)	
Concomitant medications/Blood Products	X(k)	X		X	
Efficacy (i)					
Cervical CT-Scan or MRI	X		X	X	X (h)
Chest/upper abdominal CT-Scan or MRI	X		X	X	X (h)
Other imaging if necessary	X		X	X	X (h)
Health-related quality of life					
EORTC QLQ-C30 and QLQ-H & N 35	Before randomisation within 24h		X	X	

(a) Prior to any study procedure.

(b) Within 7 days prior to first study drug treatment.

(c) CBCC performed on days 1 and 8 in arm A; on days 1, 8 and 15 in arm B

(d) Transaminases, alkaline phosphatase, total bilirubin, urea, creatinine, calculated (Cockcroft-Gault) creatinine clearance, calcium, sodium, potassium, magnesium, chloride, bicarbonate.

(e) Glucose, total protein and albumin to be performed in addition.

(f) Within 30 days after study treatment discontinuation.

(g) Until disease progression: every 6 weeks. After disease progression, every month for the first 6 months and then every 3 months until death.

At the time of the amendment PA11, no more follow-up visit will be performed.

(h) In case of treatment discontinuation for other reason than PD, all efficacy assessments must be performed every 6 weeks from time of randomisation until disease progression is documented, then survival information will be collected approximately every month for the first 6 months then every 3 months until death.

At the time of the amendment PA11, these assessments will not be performed.

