Grade 3 thrombocytopenia (platelets $\geq 25 \times 10^9/L$ and $< 50 \times 10^9/L$) with significant bleeding or requiring transfusion	First appearance : reduce one dose level Second appearance : reduce two dose levels Third appearance : stop treatment
Grade 4 thrombocytopenia (platelets $< 25 \times 10^9/L$)	
Grade 4 neutropenia (ANC $< 0.5 \times 10^9/L$) lasting ≥ 5 days	
Neutropenic infection (grade ≥ 3 neutropenia concomitant with grade ≥ 3 infection)	
Febrile neutropenia of any grade	

5.2.4.3. *Treatment modifications for non haematological toxicity*

The non haematological adverse events which may require treatment modifications include :

- stomatitis
- increased transaminases
- and less often, nausea, vomiting, diarrhoea and skin rash.

Cycle delay

Rules defining the cycle delay are the same as outlined in section 5.2.4.2.

Day 1 administration must be delayed in case of grade > 1 stomatitis or grade > 1 increase of transaminases ($> 2.5 \times ULN$). Methotrexate must not be readministered before total recovery.

If recovery requires more than 2 weeks, methotrexate should be permanently discontinued.

Dose cancellation (days 8 and 15)

Administration on days 8 and 15 in arm B must be cancelled in case of grade > 1 stomatitis or grade > 1 increase of transaminases (> 2.5 x ULN).

This protocol does not allow other cases of dosing delay of methotrexate. Any delay of a methotrexate dosing done outside of this above rule (also shown in Table 10) will be recorded as a delay and as a protocol deviation, (≥ 4 days with respect to the planned day).

Dose modifications

The table below outlines dose reduction for non-haematological toxicity.

Table 17: Dose modifications of methotrexate in Arm B for non-haematological toxicities

Non haematological toxicity after the previous administration	Dose adjustment for next administration
Stomatitis Grade 1 Grade 2 Grade ≥ 3	Maintain the same dose Decrease one dose level Decrease two dose levels
Transaminases > 2.5 x ULN and ≤ 5.0 x ULN > 5.0 x ULN and ≤ 20 x ULN	Decrease one dose level Decrease two dose levels
Decreased creatinine clearance (Cockcroft-Gault) ≤ 60 mL/min and ≥ 20 mL/min < 20 mL/min	Decrease one dose level Discontinue treatment
Other grade $\geq 3^*$ toxicities	To be adjusted as medically indicated

* except grade 3 fatigue

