7.4. EVALUATION DURING THE STUDY PERIOD

The treatment period begins on the day of randomisation and continues until 30 days after the last study treatment administration.

The following assessments need to be completed throughout the treatment period:

Table 19: Assessments during the treatment period

Assessments	Timing - Comments
PHYSICAL EXAMINATION including weight, blood pressure and pulse, temperature, performance status (WHO score)	To be performed at day 1 of each cycle.
REVIEW OF SYMPTOMS, TOXICITY AND TREATMENTS	To be performed at day 1 of each cycle. All clinical findings and results from any complementary examination should be recorded in the CRF / eCRF.
LABORATORY TESTS (1)	
Haematology	- To be performed within 24 hours on days 1 and 8 of each cycle in arm A and before each weekly administration in arm B - In case of fever or infection according to institutional standards and investigator decision.
Serum chemistry	- To be performed within 24 hours before day 1 of each cycle in both arms (except glucose, total protein and albumin every 6 weeks)
ECG	- To be performed on D1 of the first cycle before and after drug administration in both arms and then every two cycles in both arms
TUMOUR ASSESSMENT (2)	To be performed every 6 weeks (+/- 3 working days) from randomisation (regardless of the timing of treatment cycles). All sites identified at baseline must be evaluated at each tumour assessment.
Health-related QUALITY OF LIFE (EORTC QLQ-C30 and QLQ H & N 35)	To be assessed every 6 weeks

(1) Haematology: complete blood cell count.

Serum chemistry: transaminases, alkaline phosphatase, total bilirubin, total protein, albumin, urea, creatinine and calculated (Cockcroft-Gault) creatinine clearance, glucose, calcium, sodium, potassium, magnesium, chloride, bicarbonate

(2) Tumour assessment: all target lesions (measurable disease) and non-target lesions (non-measurable disease) found at baseline should be re-investigated at each tumour assessment. Additional examinations may be performed if appearance of new lesions is suspected.

- Only the lesions found at baseline must be re-investigated. The same methods of assessment used at baseline should be used throughout the study to ensure comparability (*i.e.* scans performed immediately following bolus contrast administration using a standard volume of contrast, the identical contrast agent and preferably the same scanner).

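### Methotrexate must be cancelled within a cycle for transaminases above 2.5 x ULN, but the protocol schedules transaminases only before day 1, so a first rise after day 1 need not be tested before the next dose

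*Protocol*

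**What the plan says.** **The dosing rule.** In arm A (protocol section 5.2.3.3, dose cancellation): "Administration on day 8 must be cancelled in case of grade > 1 stomatitis or grade > 1 increase of transaminases". Section 5.2.4.3 has the matching rule for the two later doses of each arm B cycle: "days 8 and 15 in arm B must be cancelled in case of grade > 1 stomatitis or grade > 1 increase of transaminases". Both sections put the transaminase limit at 2.5 x ULN. A separate rule governs the start of a cycle: "Day 1 administration must be delayed in case of grade > 1 stomatitis or grade > 1 increase of transaminases".

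**The chemistry schedule.** Table 19 (section 7.4) times serum chemistry, which includes transaminases, as follows: "To be performed within 24 hours before day 1 of each cycle in both arms (except glucose, total protein and albumin every 6 weeks". The synopsis agrees: "Tests will be performed every 3 weeks, except glucose, total protein and albumin which will be performed every 6 weeks in both arms". Table 1 marks blood chemistry on day 1 of every cycle, every 6 weeks and at end of treatment. The 6-weekly and end-of-treatment marks carry note (e): "Glucose, total protein and albumin to be performed in addition". Section 8.2.2 refers back to the flow chart and adds no timing.

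**The blood-count schedule.** Table 1 note (c) reads: "CBCC performed on days 1 and 8 in arm A; on days 1, 8 and 15 in arm B". Sections 5.2.3.2 and 5.2.4.2 both state: "Complete blood cell counts will be performed before each administration of methotrexate".

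**Repeat testing.** Section 9.1.1 asks for abnormal results to be repeated until normal or stable. It limits abnormal to results outside the normal range that are clinically significant, and leaves the frequency to the investigator.

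**The concern.** The cancellation rule is mandatory and depends on a laboratory value that cannot be judged at the bedside. A rule of that kind needs a result in hand before the dose. The protocol provides one for the day 1 transaminase rule and for every blood-count rule, but not for the within-cycle transaminase rule.

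The stake is patient safety. Section 1.1.1 names transient liver-enzyme elevation as an expected effect of methotrexate, and sections 5.2.3.3 and 5.2.4.3 list raised transaminases among the events that may require treatment modification. A site that follows the schedule exactly could give a dose that the protocol says must be cancelled.

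The later dose steps depend on the same missing information. Above 2.5 and up to 5 x ULN, Tables 12 and 17 call for one dose level down. Above 5 and up to 20 x ULN, arm A must stop methotrexate and arm B must drop two levels. None of this is triggered by a rise that is not measured.

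**Working it through.** No power, sample-size or alpha figure enters this point, and the plan gives no figure of its own to reproduce. The check compares each methotrexate dose with the tests scheduled before it.

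**Inputs**
- Methotrexate doses per three-week cycle: 2 in arm A, on days 1 and 8 (section 5.1.1); 3 in arm B, on days 1, 8 and 15 (section 5.1.2).
- Scheduled transaminases: once per cycle, before day 1 (Table 19, synopsis, Table 1).
- Scheduled blood counts: before each methotrexate dose (sections 5.2.3.2 and 5.2.4.2, Table 1 note (c)).

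**Count.** Coverage per cycle = doses with their own scheduled test before them / all methotrexate doses.

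| | Arm A | Arm B |
|---|---|---|
| Transaminases | 1/2 | 1/3 |
| Blood count | 2/2 | 3/3 |
| Doses without a scheduled transaminase test | day 8 (1/2 = 50%) | days 8 and 15 (2/3 = 67%) |

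These are counts of scheduled tests. They do not estimate risk.

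**Does another provision fill the gap?**
1. *The 6-weekly chemistry entry in Table 1.* Note (e), the synopsis and Table 19 together show that this is glucose, total protein and albumin added at alternate cycles. Nothing ties it to day 8 or day 15.
2. *The repeat rule in section 9.1.1.* It needs an abnormal, clinically significant result to start from. It can cover a rise already found on day 1, but not a first rise after an unremarkable day 1 value.
3. *SAP section 5.4.* A cycle is evaluable for biochemical toxicity with at least one test between day 2 and the next day 1. The next day 1 sample meets that, so no mid-cycle test is implied.

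**Was dose-by-dose assessment intended?** The wording of the modification tables suggests so. Table 7 (vinflunine) adjusts the next cycle for toxicity in the previous cycle. Tables 12 and 17 (methotrexate) adjust the next administration for toxicity after the previous administration. Their transaminase rows therefore need information between doses.

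**Not part of the gap.** Stomatitis, the other half of the rule, can be checked at the supervised dosing visit. Creatinine clearance is not in the cancellation rule.

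**The case against.** The best defence is that once-per-cycle chemistry is a proportionate choice. The dose-limiting toxicities reported from the phase I combination study (section 1.2.1.4) were constipation, febrile neutropenia, neutropenic infection and ileus; none was hepatic. The interim safety focus in section 11.5.6.2 names no hepatic event, and the protocol itself calls the enzyme rises transient. Counts before every dose and chemistry once per cycle fit that profile. This bears on severity, but it does not reconcile a mandatory rule with the absence of a required test.

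The rule is also not inert. Transaminases up to 2.5 x ULN meet the inclusion criterion and do not delay day 1. If such a value is clinically significant it must be repeated, and the repeat can trigger cancellation. Sites may also run chemistry on blood drawn that day.

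For the same reason, a reader might infer that a short-lived rise is never seen or that patients are routinely dosed through one. The documents support only that the test is not required, and they give no rate of within-cycle rises.

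A reader might also try to size the reach from the progression-free survival medians in Table 2. That would estimate progression-free status, not treatment status. Toxicity, refusal and investigator decision also end dosing (section 7.6), and the documents do not say how many patients were still being dosed.

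**Conclusion.** The point holds, as a minor one. The protocol forbids a within-cycle methotrexate dose above 2.5 x ULN but requires no transaminase test tied to that dose. This leaves 1 of 2 doses per cycle in arm A and 2 of 3 in arm B without a scheduled test. The exposure is confined to a first rise after an unremarkable day 1 value. A rise that persists is caught at the next day 1. One that resolves sooner may go undetected unless the site tests by local practice.

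This rests on reading the 6-weekly entry in Table 1 as added analytes at alternate cycles, which the synopsis and Table 19 support.

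Reach is small. Recruitment stopped on 16 October 2015, and SAP section 13 dates protocol version 7 to 5 February 2016, 112 days later (15 + 30 + 31 + 31 + 5). It is not shown to be zero, because amendment PA11 lets patients under treatment continue to end of treatment.

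A reader might infer some effect on the trial's result. There is none on the overall survival analysis, which does not use these measurements.

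**What to change.** For patients still on treatment, add AST and ALT to the pre-dose blood-count draw:
- arm A: on day 8, and at the day 15 recheck if a low count has deferred the day 8 dose (section 5.2.3.2);
- arm B: on days 8 and 15.

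Align the synopsis, Table 1 and Table 19 so that all three show it.

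**Cost.** Two analytes on an existing draw, with no extra visit. The schedule change may count as a substantial amendment needing ethics committee and authority submission (section 15.1), which further limits how many patients would benefit.

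**Side effect on the safety tables.** Where no dose is deferred, scheduled transaminase tests would go from one per cycle in each arm to 1 + 1 = 2 in arm A and 1 + 2 = 3 in arm B, in late cycles only. Protocol section 11.5.4.2 and the SAP's table list report worst grade by patient and by cycle. More frequent sampling finds more transient rises, so detection would differ between arms and over time. Either note this beside the worst-grade transaminase tables or also show them using day 1 values only.
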